15.3 Blinding

This is an open-label study. No masking procedure will be applied.

16 EVALUATION PARAMETERS

16.1 Study endpoints

16.1.1 Primary endpoints

16.1.1.1 Primary endpoint of Part A

- Type, number and frequency of TEAEs collected up to 24 h post-dose.

16.1.1.2 Primary endpoint of Part B

- Area under the plasma concentration-time curve of netupitant from time zero to the time of last measurable concentration or to infinity (AUC_{0-t} and $AUC_{0-\infty}$) following administration of T, at the infusion duration selected in Part A, and R administered as a 30-min diluted infusion.

16.1.2 Secondary endpoints

16.1.2.1 Secondary safety endpoints of Part A

- Vital signs (blood pressure, pulse rate), 12-lead ECG, clinical laboratory tests (blood chemistry, hematology and urinalysis), body weight and physical examination

16.1.2.2 Secondary safety endpoints of Part B

- Safety and tolerability parameters of T versus R (TEAEs, vital signs [blood pressure, pulse rate], 12-lead ECG, clinical laboratory tests (blood chemistry, hematology and urinalysis), body weight and physical examination).
- Cardiac evaluation:
 - Placebo-corrected change from baseline in HR, QT, QTcF, QTcB, PR and QRS intervals.
 - Change from baseline in HR, QT, QTcF, QTcB, PR and QRS intervals.
 - Categorical outliers for HR, QT, QTcF, QTcB, PR, and QRS intervals.
 - Frequency of changes in T-wave morphology and U-wave presence from triplicate 12-lead ECGs extracted from continuous recordings.

16.1.2.3 Secondary PK endpoints of Part A and B

For plasma fosnetupitant, netupitant and its main metabolites M1, M2 and M3, when applicable, the following parameters will be measured/calculated:

- C_0 , C_{max} , t_{max} , C_{last} , t_{last} , AUC_{0-t} (for all analytes with exception of netupitant AUC_{0-t} in Part B, which is the primary endpoint), AUC_{0-24} , λ_z , $t_{1/2}$, CL, V_z , MRT

16.1.2.4 Secondary PK endpoints of Part B only

For plasma fosnetupitant, netupitant and its main metabolites M1, M2 and M3, when applicable, the following parameters will be measured/calculated:

- AUC₀₋₁₂₀, AUC_{0-∞} (with exception of netupitant AUC_{0-∞}, which is the primary endpoint)

For plasma fosnetupitant, the following parameter will be calculated:

- RAUC_{fos/netu}

For plasma M1, the following parameter will be calculated:

- RAUC_{M1/netu}

For plasma M2, the following parameter will be calculated:

- RAUC_{M2/netu}

For plasma M3, the following parameter will be calculated:

- RAUC_{M3/netu}

16.2 Pharmacokinetic assessments

16.2.1 Pharmacokinetic parameters

The following PK parameters will be measured and/or calculated, when applicable, for plasma fosnetupitant, netupitant and its metabolites in both parts, using the validated software Phoenix WinNonlin® version 8.3.5 (13) or higher (actual version will be stated in the final report):

C ₀ :	Plasma concentration at the end of the injection or infusion
C _{max} :	Maximum plasma concentration
t _{max} :	Time to achieve C _{max}
C _{last} :	Last measurable plasma concentration above the LQL of the bioanalytical method
t _{last} :	Time of C _{last}
AUC _{0-t} :	Area under the concentration-time curve from time zero to t _{last} , calculated by the linear trapezoidal method
AUC ₀₋₂₄ :	Area under the plasma concentration-time curve from time zero to 24 h
λ _z :	Terminal elimination rate constant, calculated, if feasible, by log-linear regression using at least 3 points, C ₀ and C _{max} excluded
t _{1/2} :	Apparent terminal half-life, calculated, if feasible, as ln2/λ _z
CL:	Systemic clearance
V _z :	Apparent volume of distribution in the post-distribution phase

MRT: Mean residence time

The following PK parameters will be calculated for netupitant and its metabolites only in Part B:

AUC₀₋₁₂₀: Area under the plasma concentration-time curve from time zero to 120 h

AUC_{0-∞}: Area under the concentration-time curve from time zero to infinity, calculated, if feasible, as AUC_{0-t} + C_{last}/λ_z

%AUC_{extra}: Percentage of AUC_{0-inf} extrapolated from t_{last} to infinity as 100×[(C_{last}/λ_z)/AUC_{0-inf}]

The following PK parameter will be calculated for fosnetupitant only in Part B:

RAUC_{fos/netu}: Molecular weight-normalized fosnetupitant to netupitant AUC_{0-∞} ratio

The following PK parameter will be calculated for M1 only in Part B:

RAUC_{M1/netu}: Molecular weight-normalized M1 to netupitant AUC_{0-∞} ratio

The following PK parameter will be calculated for M2 only in Part B:

RAUC_{M2/netu}: Molecular weight-normalized M2 to netupitant AUC_{0-∞} ratio

The following PK parameter will be calculated for M3 only in Part B:

RAUC_{M3/netu}: Molecular weight-normalized M3 to netupitant AUC_{0-∞} ratio

The sampling schedule is considered adequate if the ratio AUC_{0-t}/AUC_{0-∞} equals or exceeds a factor of 0.8 (i.e., if %AUC_{extra} is <20%) for more than 80% of the individual PK profiles. This assures that the primary variable AUC_{0-t} covers a sufficient percentage of the theoretical total extent of exposure. AUC_{0-∞} values with %AUC_{extra} greater than 20% will be flagged but included in the summary statistics.

The quality of log-linear regression (and, consequently, the reliability of the extrapolated PK parameters) should be demonstrated by a determination coefficient $R^2 \geq 0.8$. Individual extrapolated parameters, when considered unreliable, will be reported as NC (not calculated).

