to 4353 h· μ g/L for doses in the interval from 19.5 mg to 390 mg. Mean systemic clearance was very high and ranged from 78.37 to 96.33 L/h, values close to the human liver blood flow. Mean volume of distribution for the pro-drug increased with ascending doses and ranged from 58.3 L (at 65 mg) up to 163.1 L (at 390 mg). The apparent terminal elimination half-life of fosnetupitant chloride hydrochloride ranged from 0.05 h to 1.24 h in the dosing interval from 32.5 mg to 390 mg. At 260 mg, the mean half-life was 0.956 h.

After dose escalation from 19.5 mg to 390 mg fosnetupitant chloride hydrochloride, the first quantifiable netupitant plasma concentrations were detected at all dose levels at mid infusion (15 min). Peak netupitant concentrations were observed at the end of infusion (30 min) at all dose levels. Following infusion of fosnetupitant chloride hydrochloride over 30 min, mean concentrations of netupitant remained nearly at the same level until 4 h and declined slowly afterwards.

Mean C_{max} and mean systemic exposure increased with ascending fosnetupitant chloride hydrochloride doses (mean C_{max} of 66 μ g/L and 1310 μ g/L, mean AUC_{0-t} of 556 h· μ g/L and 19647 h· μ g/L, and mean AUC_{0-inf} of 716 h· μ g/L and 23923 h· μ g/L for 19.5 mg and 390 mg doses, respectively).

The elimination of netupitant was slow with a long apparent terminal elimination half-life that ranged from 21 h to 182 h. Mean $t_{1/2}$ ranged from 35 h to 55 h.

The exposure to netupitant after IV administration of 260 mg fosnetupitant chloride hydrochloride (mean AUC_{0-t} of 12014 h· μ g/L and mean AUC_{0-inf} of 13854 h· μ g/L) was comparable to the mean systemic exposure to netupitant after oral administration of 300 mg netupitant (mean AUC_{0-t} of 11317 h· μ g/L and mean AUC_{0-inf} of 13899 h· μ g/L).

The systemic exposure to the 3 netupitant metabolites M1, M2 and M3 also increases with ascending fosnetupitant doses. C_{max} of M2 is higher (mean $C_{max} \pm SD$ = 178.74±84.52 ng/mL; median t_{max} = 2 h) and is achieved earlier than M1 (mean $C_{max} \pm SD$ = 23.31±9.26 ng/mL; median t_{max} = 12 h) and M3 (mean $C_{max} \pm SD$ = 46.49±16.86 ng/mL; median t_{max} = 12 h). All 3 metabolites are eliminated slowly and M1 (mean $t_{1/2} \pm SD$ = 159.54±72.62 h) shows a longer elimination half-life compared to M2 (mean $t_{1/2} \pm SD$ = 136.4±107.06 h) and M3 (mean $t_{1/2} \pm SD$ = 111.4±54.13 h) (5).

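### Part A lists half-life, clearance and related terminal parameters for netupitant and M1-M3 from 24-h profiles that cannot support them, and lists CL and Vz without the AUC0-inf they need

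*Protocol*

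**What the plan says.** Section 16.1.2.3, which covers both parts, opens with "For plasma fosnetupitant, netupitant and its main metabolites M1, M2 and M3, when applicable, the following parameters will be measured/calculated" and includes λz, t1/2, CL, Vz and MRT. Section 16.2.1 repeats the list: "The following PK parameters will be measured and/or calculated, when applicable, for plasma fosnetupitant, netupitant and its metabolites in both parts".

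The rate constant is defined as "Terminal elimination rate constant, calculated, if feasible, by log-linear regression using at least 3 points", with C0 and Cmax excluded. On acceptance, section 16.2.1 says "The quality of log-linear regression (and, consequently, the reliability of the extrapolated PK parameters) should be demonstrated by a determination coefficient" of at least 0.8. It adds that extrapolated values judged unreliable are reported as not calculated (NC), without saying what makes them so.

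AUC0-inf is handled differently. Section 16.1.2.4, headed "Secondary PK endpoints of Part B only", holds it for all five analytes. Section 16.2.1 introduces AUC0-120, AUC0-inf and %AUCextra with "The following PK parameters will be calculated for netupitant and its metabolites only in Part B".

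Tables 4.4 and 14.5.1.1 end Part A sampling at 24 h; the samples from 48 to 240 h belong to Part B only.

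**The concern.** There are two separate problems.

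1. **Sampling window.** Terminal parameters are listed for analytes whose half-lives are much longer than the Part A window. R² measures how straight the chosen points are, not whether they lie in the terminal phase. For netupitant a steep, non-terminal slope can therefore pass and be reported as t1/2.
2. **Missing input.** After a single IV dose CL is dose/AUC0-inf, and Vz is CL/λz. Both are listed for Part A, where AUC0-inf is not. If the software forms AUC0-inf internally, the extrapolated share goes unreported and the 20% flag in section 16.2.1 does not reach it.

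The practical risk is that Part A netupitant half-life and clearance stand beside Part B values from 240-h profiles under the same names, and the gap is read as real.

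**Working it through.** **Sampling.** The 30-min schedule has 11 samples (pre-dose, 30 and 45 min, 1, 1.5, 2, 3, 4, 8, 12, 24 h) and the 2-min schedule has 16. At 6 mL each this gives 66 mL and 96 mL, matching section 14.6. Only 8, 12 and 24 h follow the 4-h sample.

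**Inputs** (sections 8.2.1 and 8.2.1.1, 260 mg salt where a dose is given):
- Netupitant: Cmax 840.8 µg/L; mean AUC0-inf 13,854 h·µg/L; mean t1/2 35-55 h, individual values 21-182 h.
- M1, M2, M3: t1/2 159.54, 136.4 and 111.4 h; median tmax 12, 2 and 12 h.
- Fosnetupitant: mean t1/2 0.956 h.

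**Coverage by 24 h, in half-lives:**
- Netupitant: 24/55 = 0.44 to 24/35 = 0.69.
- M1: 24/159.54 = 0.15. M2: 24/136.4 = 0.18. M3: 24/111.4 = 0.22.
- Fosnetupitant: 24/0.956 ≈ 25.

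**Netupitant must have a faster early phase.**
- A single-phase decline with the stated Cmax and AUC would have t1/2 = ln2 × 13,854/840.8 = 11.4 h.
- A decline from Cmax at the stated half-lives alone would give AUC = 840.8 × 35/ln2 = 42,456 to 840.8 × 55/ln2 = 66,716 h·µg/L, which is 3.1 to 4.8 times the stated value.
- Even the shortest individual half-life, 21 h, gives 840.8 × 21/ln2 = 25,473, or 1.8 times.
- Section 8.2.1.1 says "mean concentrations of netupitant remained nearly at the same level until 4 h and declined slowly afterwards". A plateau strengthens the point. With a linear rise to 0.5 h and a flat level to 4 h, the area used is 840.8 × 0.5/2 + 840.8 × 3.5 = 3,153. The remaining 10,701 implies an average decline with t1/2 = ln2 × 10,701/840.8 = 8.8 h. The fast phase then falls within the samples available for fitting.

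**How large the error could be (illustration).** The speed of the early phase is not stated, so it is assumed. Cmax and AUC0-inf are fixed at the stated values, terminal t1/2 at 35, 45 or 55 h, and early t1/2 at 2, 3, 4, 5, 6 or 8 h. The curve is either biexponential from 0.5 h (18 profiles), or has 100, 90 or 80% of Cmax at 4 h and is biexponential afterwards (54 profiles). No noise is added.

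| Fit | t1/2 (h) | R² | Pass R² ≥ 0.8 |
|---|---|---|---|
| 8-12-24 h | 6.8-23.4 (12-65% of truth) | 0.87-1.00 | 72 of 72 |
| 4-8-12-24 h | 6.2-15.5 | 0.77-1.00 | 70 of 72 |

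Across both fits, CL is 1.02-1.85 times truth with the linear trapezoidal rule that section 16.2.1 names for AUC0-t, and 1.04-1.88 times with the exact area to 24 h. The true share of AUC beyond 24 h is 18-62%; the fits put it at 8-43%.

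**One profile by hand.** Take 70% of Cmax at 4 h, early t1/2 3 h and terminal t1/2 45 h. Concentrations at 8, 12 and 24 h are 311, 196 and 109 µg/L, with logs 5.740, 5.278 and 4.691. Sxx = 138.67 and Sxy = −8.554, so the slope is −0.0617 per h, t1/2 = ln2/0.0617 = 11.2 h and R² = 0.956. CL is 1.57 times truth. With 10% random scatter, 98% of such fits still pass.

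**Metabolites.** For M1 and M3, with median tmax 12 h, only the 24-h sample follows Cmax, so three points are usually not available. M2 has enough points, but at 136.4 h it falls only 1 − 0.5^(12/136.4) = 5.9% from 12 to 24 h. Assuming mono-exponential decline and 5-10% random error, 43% to 28% of 8-12-24 h fits pass R².

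**CL and Vz.** No arithmetic is needed: sections 16.1.2.3 and 16.2.1 list both for Part A, while sections 16.1.2.4 and 16.2.1 keep AUC0-inf out of it.

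**The case against.** **The wording allows values to be withheld.** The lists are qualified by *when applicable* and *if feasible*, and unreliable values may be reported as NC. R² ≥ 0.8 is stated as something fit quality should show, not as a rule that a passing value must be reported, and the SAP may add criteria. This is fair: the protocol does not force a wrong number into the tables. But it lists the parameters for these analytes in Part A, and the one reliability criterion it gives does not detect the problem for netupitant.

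**The safeguards mostly work for the metabolites.** This stands. For M1 and M3 the listing is unsupportable rather than misleading; for M2, R² rejects many profiles.

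**The size is assumed.** This also stands. Early half-lives of 2-8 h are not in the protocol, the 35-55 h range is not tied to the 260 mg dose, and several illustrative curves fall faster than the slow decline that section 8.2.1.1 describes. A different grid (early t1/2 1-6 h; decline from the end of infusion, or 50, 70 or 100% of Cmax at 4 h) also gave half-lives below truth in all 60 profiles, with 59 passing R². The bias was small (33.8 h against 35 h) only with a 1-h early phase starting at the end of infusion, which leaves 34% of Cmax at 4 h and contradicts the plateau.

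**An endpoint list does not forbid an intermediate AUC0-inf, and MRT could be truncated at the last sample.** An unreported intermediate leaves the reader unable to see how much of CL is extrapolated. An MRT truncated at 24 h cannot exceed 24 h, against 162.6 h reported for patients in section 11.2, so it would inform no better.

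**Nothing is decided on these values.** Agreed; this sets the rating.

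**Conclusion.** Wrong as written, with minor impact. Three conclusions need no modelling: 24 h covers well under one mean half-life of netupitant and about a fifth or less of the metabolites' half-lives; the stated Cmax and AUC0-inf require a faster netupitant phase before the terminal one; and CL and Vz are listed for Part A without AUC0-inf. That a fit ending at 24 h gives too short a netupitant half-life follows from the protocol's figures and its 4-h plateau. How much too short (12-65% of truth in the 8-12-24 h illustration), and the overstatement of CL, rest on assumed early-phase half-lives and are a range, not a prediction. Figure 4.1 labels Part A pharmacokinetics exploratory, and the truncation is common to all Part A arms. Duration selection rests on safety and the equivalence test on Part B data, so neither changes.

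**What to change.** In sections 16.1.2.3 and 16.2.1 and the matching synopsis list:

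- In Part A, limit λz, t1/2, CL, Vz and MRT to fosnetupitant, for which 24 h is ample.
- Add AUC0-inf for fosnetupitant in Part A. Also name fosnetupitant in the AUC0-inf entry of section 16.2.1, which now covers only netupitant and its metabolites, although section 16.1.2.4 and the fosnetupitant/netupitant AUC ratio need it.
- For netupitant and M1-M3 in Part A, report C0, Cmax, tmax, Clast, tlast, AUC0-t and AUC0-24 only.

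The cost is a wording change. The sponsor gives up descriptive values that 24-h data cannot support; Part B is planned to supply them from 240-h profiles.

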16.3 Safety assessments

Safety and general tolerability of T versus R will be based on TEAEs, physical examinations including body weight, vital signs, 12-lead ECG and routine hematology, blood chemistry and urinalysis laboratory tests.

16.3.1 Cardiodynamic ECG assessment for Part B

The following ECG parameters will be measured and calculated: HR, PR, QT, Fridericia corrected QTc (QTcF), Bazett corrected QTc (QTcB), QRS.

T-wave morphology and U-wave presence will be assessed.
Statistical methodology for the cardiac evaluation endpoints is presented in § 17.5.7.

17 STATISTICAL METHODS

The data documented in this study and the parameters measured will be evaluated and compared using classic descriptive statistics, i.e., geometric mean (PK data only), arithmetic mean, SD, CV (%), minimum, median and maximum values for quantitative variables, and frequencies for qualitative variables.

Not available data will be evaluated as “missing values”. The statistical analysis of demographic and safety data will be performed using SAS® version 9.3 (TS1M1) (13) or higher (the actual versions will be stated in the final report).

The statistical analysis of PK parameters will be performed using Phoenix WinNonlin™ version 8.3.5 (14) or higher and SAS® version 9.3 (TS1M1) or higher.

Further details of the statistical analyses and data presentations to be used in reporting the study will be provided in the Statistical Analysis Plan (SAP).

Demographic, safety, and PK analyses will be performed by the Biometry Unit of the CRO (§ 7.6), while ECG statistical analysis will be performed by the provider of continuous ECG (§ 7.5).

17.1 Analysis Sets

17.1.1 *Definitions*

A subject will be defined as screened after the signature of the informed consent, regardless of the completion of all the screening procedures.

A subject will be defined as eligible if he/she meets all the inclusion/exclusion criteria. Otherwise, he/she will be defined as a screen failure.

A subject will be defined as enrolled in the study if he/she is included in the interventional phase of the study. The enrolment will be performed through a non-randomized or randomized inclusion in the study.

An eligible but not enrolled subject will be defined as a reserve.

- Enrolled set: all enrolled subjects. This analysis set will be used for demographic, baseline and background characteristics
- Safety set: all subjects who receive at least one dose of the IMPs, including partial administration. This analysis set will be used for the safety analyses
- PK set A: all enrolled subjects who fulfill the study protocol requirements in terms of T or R_a administration and have evaluable PK data readouts, with no major deviations that may affect the PK results. This analysis set will be used for the statistical analysis of the PK results of study Part A
- PK set B: all enrolled subjects who fulfill the study protocol requirements in terms of T and R administration and have evaluable PK data readouts for the planned treatment

comparisons, with no major deviations that may affect the PK results. This analysis set will be used for the statistical analysis of the PK results of study Part B

Each subject will be coded by the CRO Biometry Unit as valid or not valid for the Safety set, PK set A and PK set B. Subjects will be evaluated according to the treatment they actually receive.

17.1.1.1 Reasons for exclusion from the PK set before bioanalysis

Reasons for the exclusion of subjects from one period in the PK set are the following:

- intake of concomitant medications or food / beverages which could render the plasma concentration-time profile unreliable
- AEs which could render the plasma concentration-time profile unreliable
- administration errors which could render the plasma concentration-time profile unreliable
- other events which could render the plasma concentration-time profile unreliable

If one of these events occurs, it will be noted in the CRF as the study is being conducted.

17.1.1.2 Reasons for exclusion from the PK set B after bioanalysis

Exclusion of subjects on the basis of PK reasons is possible only for:

- subjects with lack of any measurable concentrations or only very low plasma concentrations of netupitant. A subject is considered to have very low plasma concentrations if his/her AUC is less than 5% of netupitant geometric mean AUC (which should be calculated without inclusion of data from the outlying subject)
- subjects with implausible concentrations (i.e., different from the known, expected concentration profiles) of netupitant. The exclusion of these subjects must be justified on the basis of sound scientific reasons and mutually agreed between the CRO and the Sponsor
- subjects with non-zero baseline concentrations $> 5\%$ of C_{max}

The samples from the subjects excluded from PK set B after bioanalysis should still be assayed and the results listed. Subjects should not be excluded from PK set B if the AUC_{0-t} covers less than 80% of the $AUC_{0-\infty}$.

17.2 Sample size and power considerations

The planned number of 20 healthy subjects to be included in cohort 1 and of 10 healthy subjects to be included in each following cohort of Part A (cohorts 2, 3 and 4) of the study was not computed by statistical assumptions.

The sample size for the netupitant exposure equivalence (netupitant AUC) assessment in Part B of the study, will be 40 healthy male and female subjects in order to have 34 completed subjects. Drop-outs will not be replaced. The sample size was determined by a statistical power calculation to test equivalence based on AUC_{0-t} . The assumptions are that the expected ratio of means is 1 (Fosnetupitant 235 mg IV versus Akyenze IV injection), the cross-over ANOVA \sqrt{MSE} (ln scale) is 0.265, and α is 10% (bilateral). A sample size in each sequence group of 17 (total sample size is 34) is required to have a power of 90%.

17.3 Demographic, baseline and background characteristics

Critical demographic characteristics will be examined according to qualitative or quantitative data. Qualitative data will be summarized in contingency tables. Quantitative data will be summarized using classic descriptive statistics.

17.4 Analysis of pharmacokinetic parameters

17.4.1 Descriptive pharmacokinetics

A descriptive PK will be presented. The results will be displayed and summarized in tables and figures. Individual curves at actual sampling times and mean curves (+SD) at scheduled sampling times will be plotted. Data below the lower quantification limit (BQL) will be considered as 0 in the calculations of mean concentrations and “missing data” in individual concentration-time plots. For the estimation of PK parameters, BQL concentrations will be considered as 0 at early time points (i.e., time points before C_{max}) and “missing data” at later time points, including the terminal part of the curve. They will be presented as BQL in listings and tables. As a consequence of BQL values, calculated geometric means (if requested) could be null. For this reason, in the presence of any null value, the geometric mean will be reported as not calculated (NC).

17.4.2 Statistical comparison of pharmacokinetic parameters

According to the current FDA Guideline on the bioavailability and bioequivalence studies (9), AUC_{0-t} and $AUC_{0-\infty}$ of plasma netupitant of study Part B will be analyzed using analysis of variance (ANOVA). Before analysis, the data will be transformed using a neperian logarithmic transformation. The statistical analysis will take into account treatment, period, sequence and subject within sequence as fixed effects. The parametric point estimators (PE) for the ratios of treatments and 90% CI will be calculated using the adjusted least squares means from the ANOVA. Results for the log-transformed exposure measures will be then back-transformed to obtain point estimators (i.e., geometric mean ratio) and two-sided 90% CI as percentages.

The statistical method for testing bioequivalence is based upon the 90% CI for the T/R ratio of the least square geometric means of the parameters under consideration. Acceptance criterion

for bioequivalence will be a 90% CI of the ratio of geometric means (PE) within the 80.00 – 125.00% range.

While the equivalence of the selected T and R will be assessed based on the netupitant AUC_{0-t} and AUC_{0-∞} estimates, the T/R geometric mean ratio and the relevant 90% CI will also be calculated for other exposure measures, including netupitant AUC₀₋₁₂₀ and C_{max}. The T/R geometric mean ratio and the relevant 90% CI will also be calculated for exposure measures of M1, M2 and M3, including AUC_{0-t}, AUC_{0-∞}, AUC₀₋₁₂₀ and C_{max}.

The peak time, t_{max}, of T and R will be analyzed using a non-parametric test applied to untransformed data.

